4.2 INCLUSION CRITERIA

Subjects must meet all study Inclusion Criteria as outlined below:

- 1) Healthy adult males or females age \geq 18-40 years of age with signed informed consent.
- 2) The subject must appear able and willing to adhere to the instructions set forth in this clinical protocol.
- 3) Subject must be a habitual soft toric contact lens wearer. Habitual wearer is defined as someone who wears contact lenses for at least 6 hours a day, 5 days a week for the past 30 days.
- 4) Subject's vertex corrected spherical component of their distance refraction must be between -1.00 to -4.75D (inclusive) in each eye.
- 5) Subject's vertex corrected refractive cylinder must be between -0.75 and -1.50DC (inclusive) in each eye.
- 6) Subject's refractive cylinder axis must be 180 ± 25 and 90 ± 15 in each eye.
- 7) The subject must have visual acuity best correctable to 20/25 or better for each eye
- 8) The subject must read and sign the Informed Consent form.

Subjects meeting any of the following Exclusion Criteria will not be eligible to participate in the study:

- 1) Women who are pregnant or breastfeeding.
- 2) Any ocular or systemic allergies or diseases that may contraindicate contact lens wear.
- 3) Any ocular medications use within the last one month.
- 4) Any systemic disease, autoimmune disease, or use of medication, which may interfere with contact lens wear.
- 5) Any infectious disease (e.g., hepatitis, tuberculosis) or a contagious immunosuppressive disease (e.g., HIV), by self-report.
- 6) Habitual wearer of extended wear contact lenses.
- 7) Known sensitivity to Revitalens OcuTec®.
- 8) Any previous history of ocular and/or refractive surgery (e.g., radial keratotomy, PRK, LASIK, etc.).
- 9) A clinical finding or history of entropion, ectropion, extrusions, chalazia, recurrent styes, glaucoma, history of recurrent corneal erosions, aphakia, or moderate or above corneal distortion, by self-report.
- 10) History of binocular vision abnormality or strabismus, by self-report.
- 11) Habitual wearer of rigid gas permeable (RGP) lenses, orthokeratology lenses, or hybrid lenses (e.g. SynergEyes, SoftPerm) within the past 6 months.
- 12) Employee of investigational clinic (e.g., Investigator, Coordinator, Technician).
- 13) Participation in any contact lens or lens care product clinical trial within 14 days prior to study enrollment.

- 14) Clinically significant (grade 3 or higher) corneal edema, corneal vascularization, corneal staining, tarsal abnormalities, bulbar injection or any other abnormalities which would contraindicate contact lens wear.
- 15) Any history of a contact lens-related corneal inflammatory event within the past year that may contraindicate contact lens wear.
- 16) Any active ocular infection.
- 17) Any corneal distortion resulting from previous hard or rigid gas permeable contact lens wear.
- 18) Any fluctuations in vision due to clinically significant dry eye or other ocular conditions.

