2.1 NAME AND DESCRIPTION OF INVESTIGATIONAL PRODUCTS

The following contact lenses will be used in this study:

LENSES		
Test Article Form	Test	Control
Design / Description	senofilcon C toric	Air Optix for Astigmatism
Lot Number or Other Identifier e.g., Compass Protocol Number or Lens ID Code	[REDACTED] [REDACTED]	[REDACTED] [REDACTED] [REDACTED]
Manufacturer	JJVC	Alcon
Packaging Form	Blister	Blister
Nominal Distance Powers (D)	-1.00 to -4.50 in 0.25 steps	-1.00 to -4.50 in 0.25 steps
Nominal Cylinder Powers (D)	-0.75, -1.25	-0.75, -1.25
Nominal Base Curve @ 22 oC	8.5/14.5	8.7/14.5
Material	senofilcon C	lotrafilcon B
Cylinder Axis (°)	80, 90, 100, 10, 20, 160, 170, 180	80, 90, 100, 10, 20, 160, 170, 180
Overall Diameter (mm)	14.5	14.5

The following solutions will be used in this study:

SOLUTIONS	
Solution Name / Description	Revitalens OcuTec®Multi-Purpose Disinfecting Solution
Manufacturer	Abbott Medical Optics

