4.5 RANDOMIZATION AND MASKING

This study is a randomized, double-masked parallel group design. Each subject will be randomized to wear one of two study lenses during the study in a ratio of 1:1 following the randomization scheme provided by the JJVC biostatistician. The randomization assignment will be performed at the first visit prior to the first fitting.

The following must have occurred prior to assignment:

- Informed consent has been obtained
- Subject meets all the inclusion / exclusion criteria
- Subject history and baseline information has been collected

This will be a double masked study. The identity of the study lenses will be masked to not only the subject but also investigators involved in the data collection.

There is an inherent potential risk for unmasking. However, masking will be maintained as much as is logistically feasible. Under normal circumstances, the mask should not be broken until all subjects have completed the study and the database is finalized. Otherwise, the mask should be broken only if specific emergency treatment/course of action would be dictated by knowing the treatment status of the subject. In such cases, the investigator may, in an emergency, contact the medical monitor. In the event the mask is broken, the sponsor must be informed as soon as possible. The date, time, and reason for the unmasking must be documented in the subject record.

Subjects who have had their treatment assignment unmasked are expected to return for all remaining scheduled evaluations. A replacement subject may be enrolled if a subject discontinues from the study prematurely. The decision to enroll replacement subjects will be made by the joint agreement of the Investigator and Sponsor.

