6.	Biomicroscopy	
Slit Lamp Classification Scale (2018) will be used to grade the findings.
 
The following [REDACTED] will be used to assess specific ocular physiology in greater detail: (0.50 steps)
 
 [REDACTED] : Limbal and conjunctival redness [REDACTED] : Corneal staining [REDACTED] : Conjunctival staining 	
7	Eligibility after Baseline Examination	All responses to Inclusion Criteria questions must be answered “yes,” and all responses to Exclusion Criteria questions must be answered “no” for the subject to be considered eligible.	

VISIT 1: TREATMENT 1 - ASSIGNMENT 1			
Step	Descriptor	Details	or Appendix
1.	Lens Information	
Select lens type based on Randomization scheme
 
Select the lens powers based on the following guide:
 
 • The cylinder & axis are as close as possible to the vertex corrected refraction • Do not over-correct cylinder power • The best spherical equivalent of the toric contact lens should be as close as possible to the spherical equivalent (SE) of the subject's vertexed refraction 
For example :
 
Subject's refraction: -2.00-1.00 x180 (SE -2.50DS)
 
Lens choice A: -2.00-0.75 x 180 (SE -2.37)
 
Lens choice B: -2.25-0.75x180 (SE -2.62)
 
Lens choice A should be chosen in this example
	

Step		Descriptor	Details	or Appendix
1.		Right Lens Insertion	
The investigator or subject will place the lens on eye. If the lens is uncomfortable, inspect for damage and remove, reinsert or replace as necessary. If lens damage is present, complete the Product Quality Complaint Form and return the lens to the Sponsor. The lens will be stored in labeled vial with unpreserved saline, and clearly differentiated from the other worn lenses that will be shipped back to the Sponsor.
	
2.		Timed settling for right lens	
The investigator will start a stopwatch or timer as soon as the right lens is inserted.
 
Note: Study lenses have scribe marks at either 6 o'clock and 12 o'clock positions or 3, 6, 9 o'clock positions. Rotation measurements are made relative to a vertical reference line. Record base nasal or base temporal to the nearest degree.
 
At one (1) minute after insertion: Record the rotational position to the nearest degree
 
At three (3) minutes after insertion: Record the rotational position to the nearest degree
	

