3.		Left lens insertion	
The investigator or subject will insert the left lens. If the lens is uncomfortable, inspect for damage and remove, reinsert or replace as necessary. If lens damage is present, complete the Product Quality Complaint Form and return the lens to the Sponsor. The lens will be stored in labeled vial with unpreserved saline, and clearly differentiated from the other worn lenses that will be shipped back to the Sponsor
	
4.		Timed settling for left lens	
The investigator will note the time on the stopwatch or timer as soon as the left lens is inserted.
 
At one (1) minute after insertion: Record the rotational position to the nearest degree.
 
At three (3) minutes after insertion: Record the rotational position to the nearest degree.
	
5.		Lens settling	Allow a minimum of 10 minutes of lens settling time.	

6.	Toric Fit Evaluation	
After lens settling, record:
 
 • The rotational position to the nearest degree • Lens stability with blink • Lens stability with eye versions • Toric fit acceptable or unacceptable 
Toric lens fit will be unacceptable if lenses rotated more than 20 degrees, or lens stability is worse than 5 degrees movement with blink. If toric fit is unacceptable, proceed to final evaluation.
	
7.	Subjective spherical over refraction	
Perform subjective spherical refraction over the study contact lens and record the result in visual acuity for OD, OS. Plano or +0.25D must be achieved to continue.
	
8.	Lens modification (if needed)	
Select the reason(s) for lens change (select all that apply):
 
 • The settled lens rotation is such that one of the other available lens cylinder axis would be better (use LARS rule to determine the replacement lens cylinder axis) • The over-refraction is not plano or +0.25 in both eyes • Other (specify reason) 
If one or both lenses are modified, repeat steps 1 through 7 for one or both eyes as appropriate.
 
* If plano over-refraction cannot be achieved, the final sphere should be the most plus/least minus possible for best vision. A maximum of two lens modifications is allowed.
 
If these conditions are not met, proceed to final evaluation.
	
9.	ETDRS Visual performance	
Under high illumination and high chart luminance, record the distance high contrast visual acuity for OD, OS, OU using ETDRS charts at 4 meters.
	

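### Eligibility runs to a vertexed sphere of -4.75 D but both study lenses stop at -4.50 D, so eyes at that edge are not expected to meet the plano/+0.25 D fitting condition

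*Protocol*

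**What the plan says.** **Eligibility.** Protocol 4.2, inclusion criterion 4, with the same text in the synopsis (1.8), requires that the vertex-corrected sphere "must be between -1.00 to -4.75D (inclusive) in each eye". Criterion 5 admits cylinders from -0.75 to -1.50 D. No criterion refers to the lens powers supplied.

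**Lenses.** In Protocol 2.1 the sphere row is the same for test and control. After its leading minus sign it reads "1.00 to -4.50 in 0.25 steps". Both lenses come in cylinders of -0.75 and -1.25 D.

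**Selection.** The Visit 1 guide (Protocol 4.7.1) asks for the closest cylinder and axis and the closest spherical equivalent (SE), with the restriction "Do not over-correct cylinder power". Its worked example takes a refraction of -2.00 -1.00 x 180 and picks "Lens choice A: -2.00-0.75 x 180 (SE -2.37").

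**Over-refraction condition.** Visit 1 step 7 states: "Plano or +0.25D must be achieved to continue". Step 8 allows two lens modifications and sends subjects who do not meet the conditions to final evaluation. Its footnote adds: "If plano over-refraction cannot be achieved, the final sphere should be the most plus/least minus possible for best vision".

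**Timing.** Protocol 4.5: "The randomization assignment will be performed at the first visit prior to the first fitting". SAP 1.6 agrees.

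**The concern.** The eligibility limit reaches one quarter-dioptre step past the strongest sphere on the shelf, and the next stage of the same visit tests for exactly that shortfall. A subject can satisfy every criterion, be randomized, and then be expected to miss a condition that no supplied sphere can correct.

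What follows depends on how steps 7 and 8 are read.

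- **Strict reading.** The subject leaves after randomization. Rotation and blink stability have been recorded at step 6. The exit comes before the lens fit assessment (step 13), the Snellen acuity with study lenses (dispensing step 1) and the first scheduled post-wear corneal staining (Visit 2, step 14). These feed three of the five co-primary endpoints. The final evaluation calls for acuity with refraction, not for these measures, and missing values are not imputed (Protocol 9.5; SAP 5.1.2). The subject is not a completer, so is also outside the per-protocol set used for the secondary analyses.
- **Footnote reading.** The subject may go on with a slightly under-minused lens, provided the 20/30 and acceptable-vision dispensing conditions are met.

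**Working it through.** **Inputs.** Eligible sphere -1.00 to -4.75 D and cylinder -0.75 to -1.50 D (Protocol 4.2). Lens sphere -1.00 to -4.50 D in 0.25 D steps, lens cylinder -0.75 or -1.25 D (2.1). Selection guide and over-refraction condition from 4.7.1. Assumption: vertexed values fall in quarter-dioptre steps.

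**Formulas.** SE = sphere + cylinder/2. Lens cylinder = the closest one supplied that does not exceed the eye's. Lens sphere = the one giving the closest SE, with ties going to less minus, as in the protocol's example. Nominal residual = eye SE minus lens SE; a negative value means the eye still wants minus.

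**The protocol's own example.** Eye: -2.00 + (-1.00/2) = -2.50. Lens A: -2.00 + (-0.75/2) = -2.375. Lens B: -2.25 + (-0.75/2) = -2.625. Both are 0.125 D away and the less minus one, A, is chosen. This reproduces the protocol (which truncates to -2.37 and -2.62). The residual accepted is -2.50 - (-2.375) = -0.125 D.

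**Edge of the range.**

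| Eye | Eye SE | Best guide-compliant lens | Lens SE | Residual |
|---|---|---|---|---|
| -4.75 / -0.75 | -5.125 | -4.50 / -0.75 | -4.875 | -0.25 |
| -4.75 / -1.00 | -5.25 | -4.50 / -0.75 | -4.875 | -0.375 |
| -4.75 / -1.25 | -5.375 | -4.50 / -1.25 | -5.125 | -0.25 |
| -4.75 / -1.50 | -5.50 | -4.50 / -1.25 | -5.125 | -0.375 |

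At every quarter-dioptre sphere from -1.00 to -4.50 D the same four cylinders leave 0.00, -0.125, 0.00 and -0.125 D. The gap is therefore at the strong end only.

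**Can a modification close it?** Under the guide, no, because there is no stronger sphere. Outside the guide, over-correcting the cylinder with -4.50/-1.25 (SE -5.125) gives -5.125 - (-5.125) = 0.00 D for cylinder -0.75 and -5.25 - (-5.125) = -0.125 D for cylinder -1.00. For cylinders -1.25 and -1.50 it is already the lens in the table, and nothing supplied does better.

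**If the sphere is not rounded** (cylinders still in quarter steps). Between -4.50 and -4.75 D the residual is sphere + 4.50 for cylinders -0.75 and -1.25, and 0.125 D more minus for -1.00 and -1.50. At -4.60 D that is -0.10 or -0.225 D. The size exceeds 0.125 D only beyond -4.625 D (cylinder -0.75 or -1.25) or beyond -4.50 D (cylinder -1.00 or -1.50). The affected band is narrower for half the cylinders, but it does not vanish.

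**The case against.** The strongest reply is the step 8 footnote. Naming a final sphere for eyes that do not reach plano has little purpose if all of them exit, and the dispensing conditions (20/30 or better, vision acceptable to the subject, acceptable fit) do not repeat the plano requirement. This stands as a fair reading, so the exit cannot be stated as certain. But the footnote gives a sphere without saying that the subject continues, and it sits beside the step 7 wording and the instruction to go to final evaluation. It does not make the eye meet step 7.

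Second, the limit may be deliberate tolerance. Cylinder eligibility also runs 0.25 D past the strongest lens cylinder, and the axis limits run 5 degrees past the axes supplied. That is plausible, but only sphere power has its own over-refraction condition, so a tolerance here is one that the next step is expected to reject.

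Third, the selection text is only a guide and over-refraction is subjective. Some eyes at the edge may read plano, and off-guide choices rescue two of the four cylinders. This limits the claim to what is expected nominally; it leaves cylinders -1.25 and -1.50 without a remedy.

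A reader might infer that the problem comes to light only after randomization. The documents do not support that. The refraction is recorded at baseline step 5, before assignment, so a site can see the mismatch coming. What is missing at that point is any criterion on which to exclude the eye; only the formal test comes later.

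**Conclusion.** The mismatch holds and is minor. On quarter-dioptre values, an eye at -4.75 D is left with a nominal -0.25 or -0.375 D under the selection guide, against 0.00 or -0.125 D everywhere else in the range, and is not expected to reach plano or +0.25 D. The arithmetic is secure given that assumption. The consequence is less so, because it turns on whether step 7 or the step 8 footnote governs.

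A reader might go further and infer biased arms, lost power or a material number of lost subjects. The documents do not support any of these. Both lenses have the same power range, so nothing in the mismatch favours an arm. No refraction distribution is given, so the number of affected subjects is unknown and could be near zero. The plan allows replacement subjects and about 15% dropout. An exiting subject can still enter the safety set used for the primary analyses, and the last follow-up form required by Protocol 5.1 may capture some data. What remains is a foreseeable and avoidable source of post-randomization exits or under-minused wear.

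**What to change.** Change the sphere limit from -4.75 to -4.50 D in Protocol 4.2 and 1.8. With quarter-dioptre cylinders the worst nominal residual is then 0.125 D, whether or not the sphere is rounded. That is the level the protocol's worked example accepts when choosing a lens. It removes the expected shortfall but not every step 7 failure: an eye at -4.50 D that over-refracts more minus still has no stronger sphere.

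The cost is a one-line amendment in two places and slightly narrower recruitment. Supplying a -4.75 D sphere instead would also close the gap (residuals return to 0.00 or -0.125 D). With eight axes listed ("80, 90, 100, 10, 20, 160, 170, 180") and two cylinders, that means up to 2 x 8 = 16 added parameters per arm, so the eligibility edit is the cheaper route.

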4.4 STUDY DESIGN, TIME AND EVENT SCHEDULE, FLOWCHART

The study is a multi-site, 5-visit dispensing, bilateral two arm parallel group design, double-masked clinical trial. Approximately 270 eligible subjects will be enrolled and a minimum of 230 are targeted to complete the study.

Description of study timing:

Visit	Description	≈ Duration
1	Enrollment visit: Informed consent, eligibility criteria, baseline data, trial fitting, dispensing, and visual performance.	2.5 hours
2	6-9 days from Visit 1: Follow-up visit for the study lens: Subjective responses, VA, fitting characteristics, surface characteristics, physiology.	1.0 hour
3	6-9 days from Visit 2: Follow-up visit for the study lens: Subjective responses, VA, visual performance, fitting characteristics, surface characteristics, physiology.	1.5 hours
4	6-9 days from Visit 3: Follow-up visit for the study lens: Subjective responses, VA, fitting characteristics, surface characteristics, physiology.	1.0 hour
5	6-9 days from Visit 4: Follow-up visit for the study lens: Subjective responses, VA, visual performance fitting characteristics, surface characteristics, physiology.	1.5 hours

4.4.1 TIME AND EVENT SCHEDULE

Event	Visit 1 Day 0 (Consent, Baseline, Study Lens Dispense)	Visit 2 6-9 days after Visit 1 (Study Lens Follow-Up)	Visit 3 6-9 days after Visit 2 (Study Lens Follow-Up)	Visit 4 6-9 days after Visit 3 (Study Lens Follow-Up)	Visit 5 6-9 days after Visit 4 (Study Lens Follow-Up; Final Evaluation)
Study Informed Consent	X				
Demographics	X				
Medical History	X	X	X	X	X
Contact Lens History	X				
Inclusion/Exclusion Criteria	X				
PRO Questionnaire	X	X	X	X	X
Ocular Symptoms	X	X	X	X	X
Subjective Refraction	X				
Slit Lamp Findings	X	X	X	X	X
Lens (test article) Fitting	X				
Spherical Over-Refraction	X				X
Snellen Visual Acuity	X	X	X	X	X
Visual Performance (ETDRS)	X		X		X
Lens Fit Assessment	X	X	X	X	X
Lens Surface Evaluation	X	X	X	X	X
Lens Wettability	X	X	X	X	X
Lens Removal		X	X	X	X
Lens Insertion	X	X	X	X	
Dispense Lens	X				
Compliance / Wear Time		X	X	X	X
Final Evaluation Form					X
Adverse Event Review	X	X	X	X	X
Concomitant Medication Review	X	X	X	X	X
Study Completion					X

4.5 RANDOMIZATION AND MASKING

This study is a randomized, double-masked parallel group design. Each subject will be randomized to wear one of two study lenses during the study in a ratio of 1:1 following the randomization scheme provided by the JJVC biostatistician. The randomization assignment will be performed at the first visit prior to the first fitting.

The following must have occurred prior to assignment:

- Informed consent has been obtained
- Subject meets all the inclusion / exclusion criteria
- Subject history and baseline information has been collected

This will be a double masked study. The identity of the study lenses will be masked to not only the subject but also investigators involved in the data collection.

There is an inherent potential risk for unmasking. However, masking will be maintained as much as is logistically feasible. Under normal circumstances, the mask should not be broken until all subjects have completed the study and the database is finalized. Otherwise, the mask should be broken only if specific emergency treatment/course of action would be dictated by knowing the treatment status of the subject. In such cases, the investigator may, in an emergency, contact the medical monitor. In the event the mask is broken, the sponsor must be informed as soon as possible. The date, time, and reason for the unmasking must be documented in the subject record.

Subjects who have had their treatment assignment unmasked are expected to return for all remaining scheduled evaluations. A replacement subject may be enrolled if a subject discontinues from the study prematurely. The decision to enroll replacement subjects will be made by the joint agreement of the Investigator and Sponsor.

4.6 WEAR AND REPLACEMENT SCHEDULES, INCLUDING FORM, PACKAGING AND LABELING

Wear Schedule: Daily Wear, Monthly replacement

Test Article Packaging Description: Blister packaging in sterile packing solution

Labeling: Investigational

4.7 DETAILED STUDY PROCEDURES

4.7.1 SEQUENCE OF EVENTS

Visit 1: Enrollment Visit, Baseline Evaluation and Dispensing Trial 1

Subjects should present to Visit 1 wearing their habitual contact lenses

SCREENING INFORMATION			
Step	Descriptor	Details	or Appendix
1.	Statement of Informed Consent	Each subject must read, understand and sign the Statement of Informed Consent before being enrolled in the study. The Principal Investigator or designee conducting the informed consent discussion must also sign the consent form. Note: The subject must be provided with a signed copy of this document.	
2.	Demographics	Age, gender, race and ethnicity	
3.	Case History	Record the subject's medical and ocular history and concomitant medications.	
4.	Activity History	Record the subject's responses to questions regarding his/her daily activities, device usage and lifestyle.	
5.	Habitual Contact Lens Type	Record the following information with regard to the subject's habitual contact lenses: 
• Lens type• Base curve, diameter, and power• Lens care regimen• Modality• Approximate prescription date	
6.	Wear Time	Record the subject's average wear time (WT) and comfortable wear time (CWT).	
7.	Eligibility at Screening	All responses to Inclusion Criteria questions must be answered "yes," and all responses to Exclusion Criteria questions must be answered "no" for the subject to be considered eligible.	

BASELINE INFORMATION			
Step	Descriptor	Details	or Appendix
1.	Baseline CLUE	Subject will complete the baseline CLUE questionnaire regarding their own contact lens experience.	
2.	GSI Background Questionnaire	Subject will complete GSI questions regarding their experiences with their habitual lenses.	
3.	Distance visual acuity	Record the distance Snellen visual acuity for OD, OS, OU. Subject must keep reading smaller lines until less than half of the letters are correctly identified.	
4.	Subject-Reported Ocular Symptoms	Record Subject Reported Ocular Symptoms or Problems	
5.	Subjective spherocylinder refraction	Perform binocular subjective best spherocylinder refraction and record the best corrected visual acuity for OD, OS, OU. Subject must keep reading smaller lines until less than half the letters are correctly identified.	
6.	Biomicroscopy	
Slit Lamp Classification Scale (2018) will be used to grade the findings.
 
The following [REDACTED] will be used to assess specific ocular physiology in greater detail: (0.50 steps)
 
 [REDACTED] : Limbal and conjunctival redness [REDACTED] : Corneal staining [REDACTED] : Conjunctival staining 	
7	Eligibility after Baseline Examination	All responses to Inclusion Criteria questions must be answered “yes,” and all responses to Exclusion Criteria questions must be answered “no” for the subject to be considered eligible.	

VISIT 1: TREATMENT 1 - ASSIGNMENT 1			
Step	Descriptor	Details	or Appendix
1.	Lens Information	
Select lens type based on Randomization scheme
 
Select the lens powers based on the following guide:
 
 • The cylinder & axis are as close as possible to the vertex corrected refraction • Do not over-correct cylinder power • The best spherical equivalent of the toric contact lens should be as close as possible to the spherical equivalent (SE) of the subject's vertexed refraction 
For example :
 
Subject's refraction: -2.00-1.00 x180 (SE -2.50DS)
 
Lens choice A: -2.00-0.75 x 180 (SE -2.37)
 
Lens choice B: -2.25-0.75x180 (SE -2.62)
 
Lens choice A should be chosen in this example
	

Step		Descriptor	Details	or Appendix
1.		Right Lens Insertion	
The investigator or subject will place the lens on eye. If the lens is uncomfortable, inspect for damage and remove, reinsert or replace as necessary. If lens damage is present, complete the Product Quality Complaint Form and return the lens to the Sponsor. The lens will be stored in labeled vial with unpreserved saline, and clearly differentiated from the other worn lenses that will be shipped back to the Sponsor.
	
2.		Timed settling for right lens	
The investigator will start a stopwatch or timer as soon as the right lens is inserted.
 
Note: Study lenses have scribe marks at either 6 o'clock and 12 o'clock positions or 3, 6, 9 o'clock positions. Rotation measurements are made relative to a vertical reference line. Record base nasal or base temporal to the nearest degree.
 
At one (1) minute after insertion: Record the rotational position to the nearest degree
 
At three (3) minutes after insertion: Record the rotational position to the nearest degree
	
3.		Left lens insertion	
The investigator or subject will insert the left lens. If the lens is uncomfortable, inspect for damage and remove, reinsert or replace as necessary. If lens damage is present, complete the Product Quality Complaint Form and return the lens to the Sponsor. The lens will be stored in labeled vial with unpreserved saline, and clearly differentiated from the other worn lenses that will be shipped back to the Sponsor
	
4.		Timed settling for left lens	
The investigator will note the time on the stopwatch or timer as soon as the left lens is inserted.
 
At one (1) minute after insertion: Record the rotational position to the nearest degree.
 
At three (3) minutes after insertion: Record the rotational position to the nearest degree.
	
5.		Lens settling	Allow a minimum of 10 minutes of lens settling time.	

6.	Toric Fit Evaluation	
After lens settling, record:
 
 • The rotational position to the nearest degree • Lens stability with blink • Lens stability with eye versions • Toric fit acceptable or unacceptable 
Toric lens fit will be unacceptable if lenses rotated more than 20 degrees, or lens stability is worse than 5 degrees movement with blink. If toric fit is unacceptable, proceed to final evaluation.
	
7.	Subjective spherical over refraction	
Perform subjective spherical refraction over the study contact lens and record the result in visual acuity for OD, OS. Plano or +0.25D must be achieved to continue.
	
8.	Lens modification (if needed)	
Select the reason(s) for lens change (select all that apply):
 
 • The settled lens rotation is such that one of the other available lens cylinder axis would be better (use LARS rule to determine the replacement lens cylinder axis) • The over-refraction is not plano or +0.25 in both eyes • Other (specify reason) 
If one or both lenses are modified, repeat steps 1 through 7 for one or both eyes as appropriate.
 
* If plano over-refraction cannot be achieved, the final sphere should be the most plus/least minus possible for best vision. A maximum of two lens modifications is allowed.
 
If these conditions are not met, proceed to final evaluation.
	
9.	ETDRS Visual performance	
Under high illumination and high chart luminance, record the distance high contrast visual acuity for OD, OS, OU using ETDRS charts at 4 meters.
	
10.	CLUE Post-Fit Questionnaire	
Subject will complete the CLUE Questionnaire regarding vision and comfort.
	
11.	GSI Questionnaire	
Subject will complete GSI questions regarding their experiences with the study lenses.
	
12.	Subject-Reported Ocular Symptoms	
Record Subject Reported Ocular Symptoms or Problems
	

13.	Lens Fit Assessment	
The general lens fit characteristics will be recorded for both study lenses. These include lens position (centration, limbal exposure, edge lift), and movement (primary and up gaze as well as push-up).
 
Fit acceptability is defined as:
 
 • No limbal exposure (presence of clear cornea) in primary gaze or with extreme eye movements. • No edge Lift • No insufficient/excessive, unacceptable movement in all three movement assessments (Primary Gaze, Upgaze and Josephson Push-up). If lens movement is insufficient and unacceptable in primary gaze and upgaze but is acceptable with the Josephson Push-up technique, the fit will be deemed acceptable. 
*Note: If the lens fit is deemed unacceptable, discontinue the subject and proceed to final evaluation.
	
14.	Lens Deposits	
Front and Back Surface Lens Deposits Back Trapped Debris and Mucin Plugs Lens damage
	
15.	Lens Wettability	Subjective Lens Surface Wettability	

The study lenses being worn will be dispensed.

Step	Descriptor	Details	or Appendix
1.	Distance visual acuity	Record the distance Snellen visual acuity for OD, OS, OU. Subject must keep reading smaller lines until less than half of the letters are correctly identified. Subject must be 20/30 or better OD and OS to continue.	
2.	Dispensing eligibility	Lenses may be dispensed if these conditions are satisfied: 
 • The quality of vision is acceptable to the subject • The lens fit was found to be acceptable. 	
3.	Patient Instruction Guide	Confirm that the subject has received a Patient Instruction Guide. Eye-Cept® rewetting drops may be used as needed by the subjects if lenses become dry during use.	
4.	Lens Care Regimen	Revitalens Ocutec® will be the multipurpose solution for the study. The multipurpose solution is used to rub, rinse and store the lenses when they are not being worn.	
5.	Follow-up visit scheduling	An appointment for the next visit should be made for approximately 1 week (6 to 9 days) after the dispensing visit. Subjects should be advised to wear the study lenses eight hours each day and to the follow-up visit, after a minimum of 8 hours wear that day .	

VISIT 2: Subjects must present to Visit 2 having worn the study lenses for at least 8 hours.

VISIT 2: TREATMENT 1 - FOLLOW-UP 1 (1-WEEK)		
Step	Descriptor	Details or Appendix
1.	Concomitant Medication and Medical History Review	Record any changes in concomitant medications or health status since the last visit.
2.	Contact lens wear times	Record the current wear time (WT) and comfortable wear time (CWT).
3.	Compliance	Record the subject's compliance with wearing the study lenses. Note whether the subject chose to rub the lenses clean after use.
4.	Subject-reported Ocular Symptoms	Record Subject Reported Ocular Symptoms or Problems
5.	CLUE Questionnaire	Subject will complete the Contact Lens User Experience questionnaire regarding their experiences with the study lenses
6.	GSI Questionnaire	Subject will complete GSI questions regarding their experiences with the study lenses.
7.	Distance visual acuity	Record the distance Snellen visual acuity for OD, OS, OU. Subject must keep reading smaller lines until less than half the letters are correctly identified
8.	Toric Fit Evaluation	
Record:
 
 • The rotational position to the nearest degree • Lens stability with blink • Lens stability with eye versions • Toric fit acceptable or unacceptable 
Toric lens fit will be unacceptable if lenses rotated more than 20 degrees, or lens stability is worse than 5 degrees movement with blink. If toric fit is unacceptable, proceed to final evaluation.

9.	Lens Fit Assessment	
The general lens fit characteristics will be recorded for both study lenses. These include lens position (centration, limbal exposure, edge lift), and movement (primary and up gaze as well as push-up).
 
Fit acceptability is defined as:
 
 • No limbal exposure (presence of clear cornea) in primary gaze or with extreme eye movements. • No edge lift • No insufficient/excessive, unacceptable movement in all three movement assessments (Primary Gaze, Upgaze and Josephson Push-up). If lens movement is insufficient and unacceptable in primary gaze and upgaze but is acceptable with the Josephson Push-up technique, the fit will be deemed acceptable. 
*Note: If the lens fit is deemed unacceptable, discontinue the subject and proceed to final evaluation

10.	Lens Deposits	Front and Back Surface Lens Deposits Back Trapped Debris and Mucin Plugs Lens damage (draw and describe)	[REDACTED] [REDACTED]
11.	Lens Wettability	Subjective Lens Surface Wettability	[REDACTED]
12.	Conjunctival Hyperemia	Record Limbal and Bulbar Conjunctival Hyperemia findings	[REDACTED]
13.	Lens Removal	The subject will remove lenses. Lenses will be saved in lens case with Revitalens OcuTec® Note: Subject should not rub lenses.	
14.	Biomicroscopy	Slit Lamp Classification Scale ([REDACTED] will be used to grade the findings. The following CTP's will be used to assess specific ocular physiology in greater detail: (0.50 steps) 
 • [REDACTED] : Corneal staining • [REDACTED] : Conjunctival staining Note: Subject must be free of any FDA grade 3 or greater slit lamp findings with no active ocular infection/inflammation.	[REDACTED] [REDACTED] [REDACTED]
15.	Eye Rinse	The investigator or clinical staff will rinse the subject's eyes thoroughly with unpreserved saline.	
16.	Lens Insertion	Subjects will remove the lenses from the lens case and re-insert the lenses.	
17.	Visual Acuity	Record the distance Snellen visual acuity with their study lenses correction in place for OD, OS, OU. Subject must keep reading smaller lines until less than half of the letters are correctly identified. Subject must be 20/30 or better OD and OS to continue.	[REDACTED]
18.	Follow-up visit scheduling	An appointment for the next visit should be made for approximately 1 week (6 to 9 days) after the follow-up visit. Subjects should be advised to wear the study lenses eight hours each day and to the follow-up visit, after a minimum of 8 hours wear that day .	

VISIT 3: Subjects must present to Visit 3 having worn the study lenses for at least 8 hours.

VISIT 3: TREATMENT 1- FOLLOW-UP 2 (2-WEEK)		
Step	Descriptor	Details
1.	Concomitant Medication and Medical History Review	Record any changes in concomitant medications or health status since the last visit.
2.	Contact lens wear times	Record the current wear time (WT) and comfortable wear time (CWT).
3.	Compliance	Record the subject's compliance with wearing the study lenses. Note whether the subject chose to rub the lenses clean after use..
4.	Subject-reported Ocular Symptoms	Record Subject Reported Ocular Symptoms or Problems
5.	CLUE Questionnaire	Subject will complete the Contact Lens User Experience questionnaire regarding their experiences with the study lenses.
6.	GSI Questionnaire	Subject will complete GSI questions regarding their experiences with the study lenses.
7.	Distance visual acuity	Record the distance Snellen visual acuity for OD, OS, OU. Subject must keep reading smaller lines until less than half the letters are correctly identified
8.	ETDRS Visual performance	Under high illumination and high chart luminance record the distance high contrast visual acuity for OD, OS, OU using ETDRS charts at 4 meters.
9.	Toric Fit Evaluation	
Record:
 
 • The rotational position to the nearest degree • Lens stability with blink • Lens stability with eye versions • Toric fit acceptable or unacceptable 
Toric lens fit will be unacceptable if lenses rotated more than 20 degrees, or lens stability is worse than 5 degrees movement with blink. If toric fit is unacceptable, proceed to final evaluation.

